## 10.6. Appendix 6: ECG Findings of Potential Clinical Concern

| ECG Findings That May Qualify as AEs  |
|--|
| 

Marked sinus bradycardia (rate <40 bpm) lasting minutes.

New PR interval prolongation >280 msec.

New prolongation of QTcF to >480 msec (absolute) or by <math>\geq</math>60 msec from baseline.

New-onset atrial flutter or fibrillation, with controlled ventricular response rate: ie, rate <120 bpm.

New-onset type I second-degree (Wenckebach) AV block of >30 seconds' duration.

Frequent PVCs, triplets, or short intervals (<30 seconds) of consecutive ventricular complexes.

   |
| ECG Findings That May Qualify as SAEs   |
| 

QTcF prolongation >500 msec.

New ST-T changes suggestive of myocardial ischemia.

New-onset left bundle branch block (QRS >120 msec).

New-onset right bundle branch block (QRS >120 msec).

Symptomatic bradycardia.

Asystole:

In awake, symptom-free participants in sinus rhythm, with documented periods of asystole <math>\geq</math>3.0 seconds or any escape rate <40 bpm, or with an escape rhythm that is below the AV node.

In awake, symptom-free participants with atrial fibrillation and bradycardia with 1 or more pauses of at least 5 seconds or longer.

Atrial flutter or fibrillation, with rapid ventricular response rate: rapid = rate >120 bpm.

Sustained supraventricular tachycardia (rate >120 bpm) ("sustained" = short duration with relevant symptoms or lasting >1 minute).

 |

- Ventricular rhythms >30 seconds' duration, including idioventricular rhythm (heart rate <40 bpm), accelerated idioventricular rhythm (HR >40 bpm to <100 bpm), and monomorphic/polymorphic ventricular tachycardia (HR >100 bpm (such as torsades de pointes)).
- Type II second-degree (Mobitz II) AV block.
- Complete (third-degree) heart block.

#### **ECG Findings That Qualify as SAEs**

- Change in pattern suggestive of new myocardial infarction.
- Sustained ventricular tachyarrhythmias (>30 seconds' duration).
- Second- or third-degree AV block requiring pacemaker placement.
- Asystolic pauses requiring pacemaker placement.
- Atrial flutter or fibrillation with rapid ventricular response requiring cardioversion.
- Ventricular fibrillation/flutter.
- At the discretion of the investigator, any arrhythmia classified as an adverse experience.

[figure not shown]
The enumerated list of major events of potential clinical concern are recommended as “alerts” or notifications from the core ECG laboratory to the investigator and Pfizer study team, and not to be considered as all inclusive of what to be reported as AEs/SAEs.

## 10.7. Appendix 7: Abbreviations

The following is a list of abbreviations that may be used in the protocol.

| Abbreviation        | Term   |
|---------------------|--|
| Abs                 | absolute   |
| ADA                 | antidrug antibodies  |
| ADCC                | antibody dependent cell-mediated cytotoxicity  |
| ADL                 | activity of daily living   |
| AE                  | adverse event  |
| ALT                 | alanine aminotransferase   |
| AST                 | aspartate aminotransferase   |
| AUC                 | area under the curve   |
| AUC 168H | area under the curve from the time of dose administration up to 168 hours  |
| AUC inf  | area under the serum concentration time profile from time zero extrapolated to infinite time   |
| CCI                 |  |
| AUC last | area under the serum concentration time profile from time zero to the time of the last quantifiable concentration (C last ) |
| CCI                 |  |
| AV                  | atrioventricular   |
| BMI                 | body mass index  |
| BP                  | blood pressure   |
| bpm                 | beats per minute   |
| BUN                 | blood urea nitrogen  |
| C1q                 | complement component 1q  |
| C av     | average concentration  |
| CDC                 | complement-dependent cytotoxicity  |
| CFR                 | Code of Federal Regulations  |
| CIOMS               | Council for International Organizations of Medical Sciences  |
| CK                  | creatine kinase  |
| CKD                 | chronic kidney disease   |
| CL                  | clearance  |
| CCI                 |  |
| C last   | last quantifiable concentration  |
| C max    | maximum observed concentration   |
| CCI                 |  |
| CO 2     | carbon dioxide (bicarbonate)   |
| COPD                | chronic obstructive pulmonary disease  |
| COVID-19            | coronavirus disease 2019   |
| CRF                 | case report form   |
| CRO                 | contract research organization   |
| CRU                 | clinical research unit   |

PFIZER CONFIDENTIAL

| Abbreviation     | Term  |
|------------------|---|
| CSR              | clinical study report   |
| CT               | clinical trial  |
| CYP              | Cytochrome P450   |
| DC               | discontinuation   |
| DILI             | drug-induced liver injury   |
| DMC              | data monitoring committee   |
| CCI              |   |
| DNA              | deoxyribonucleic acid   |
| EC               | ethics committee  |
| ECC              | emergency contact card  |
| ECG              | electrocardiogram   |
| eCRF             | electronic case report form   |
| EDB              | exposure during breastfeeding   |
| EDP              | exposure during pregnancy   |
| EMA              | European Medicines Agency   |
| E max | maximum effect  |
| ET               | early termination   |
| EU               | European Union  |
| EudraCT          | European Clinical Trials Database   |
| Fc $\gamma$      | fragment crystallizable gamma   |
| FIH              | first in human  |
| FSH              | follicle-stimulating hormone  |
| FU               | follow-up   |
| GCP              | Good Clinical Practice  |
| GDF-15           | growth differentiation factor 15  |
| GDNF             | glial cell-derived neurotrophic factor                                      |
| GFRAL            | glial cell-derived neurotrophic factor (GDNF) family receptor $\alpha$ like |
| GGT              | gamma-glutamyl transferase  |
| GLP              | Good Laboratory Practice  |
| HBcAb            | hepatitis B core antibody   |
| HBsAg            | hepatitis B surface antigen   |
| HCVAb            | hepatitis C antibody  |
| HIV              | human immunodeficiency virus  |
| HR               | heart rate  |
| HRT              | hormone replacement therapy   |
| IB               | investigator brochure   |
| ICD              | informed consent document   |
| ICH              | International Council for Harmonisation                                     |
| ID               | identification  |
| IgG1             | immunoglobulin G1   |
| IND              | investigational new drug application  |

PFIZER CONFIDENTIAL

| Abbreviation | Term  |
|--------------|---|
| INR          | international normalized ratio                |
| IP           | investigational product                       |
| IPAL         | Investigational Product Accountability Log    |
| IRB          | institutional review board                    |
| IV           | intravenous                                   |
| $k_{el}$     | terminal phase rate constant                  |
| LFT          | liver function test                           |
| mAb          | monoclonal antibody                           |
| MCH          | mean corpuscular hemoglobin                   |
| MCHC         | mean corpuscular hemoglobin concentration     |
| MCV          | mean corpuscular volume                       |
| MPV          | mean platelet volume                          |
| N            | number  |
| N/A          | not applicable                                |
| NAb          | neutralizing antibodies                       |
| NOAEL        | no observed adverse effect level              |
| PD           | pharmacodynamic(s)                            |
| PE           | physical exam                                 |
| pH           | potential of hydrogen                         |
| PK           | pharmacokinetic(s)                            |
| POC          | proof of concept                              |
| PR           | pulse rate                                    |
| PT           | prothrombin time                              |
| PVC          | premature ventricular contraction             |
| Q            | distributive clearance                        |
| Q3W          | administered every 3 weeks                    |
| QT           | Q wave interval                               |
| QTcF         | corrected QT (Fridericia method)              |
| qual         | qualitative                                   |
| RBC          | red blood cell                                |
| SAE          | serious adverse event                         |
| SAP          | statistical analysis plan                     |
| SARS         | Severe Acute Respiratory Syndrome             |
| SC           | subcutaneous                                  |
| SCr          | serum creatinine                              |
| SoA          | schedule of activities                        |
| SOP          | standard operating procedure                  |
| SRSD         | single reference safety document              |
| SToD         | Study Team on Demand                          |
| SUSAR        | suspected unexpected serious adverse reaction |
| $t_{1/2}$    | half-life                                     |
| TBili        | total bilirubin                               |

PFIZER CONFIDENTIAL

| Abbreviation     | Term   |
|------------------|--|
| TEAE             | treatment-emergent adverse event               |
| TGF $\beta$      | transforming growth factor beta                |
| THC              | tetrahydrocannabinol                           |
| T max | time for C max                      |
| TPPA             | Treponema pallidum particle agglutination test |
| ULN              | upper limit of normal                          |
| US               | United States                                  |
| CCI              | [REDACTED]                                     |
| WBC              | white blood cell                               |
| WOCBP            | women of childbearing potential                |

1. VERSION HISTORY

Table 1. Summary of Changes

Version/ Date	Associated Protocol Amendment	Rationale	Specific Changes
1 18 May 2022	Original 22 Apr 2022	N/A	N/A

2. INTRODUCTION

The purpose of this study is to evaluate the pharmacokinetics (PK), **CC1** safety, and tolerability of ponsegromab following 100 mg and 400 mg single subcutaneous (SC) dose in healthy adult Chinese participants. Results from this study will be used to inform clinical development of ponsegromab in China, to facilitate China's participation in global pivotal studies, and to support China registration of ponsegromab.

This statistical analysis plan (SAP) provides the detailed methodology for summaries and statistical analyses of the data to be collected in Study C3651012. This document may modify the plans outlined in the protocol; however, any major modifications of the primary endpoints definitions or their analyses will also be reflected in a protocol amendment.

2.1. Modifications to the Analysis Plan Described in the Protocol

Not applicable.

2.2. Study Objectives, Endpoints, and Estimands

There are no estimands for this study.

Objectives	Endpoints
Primary: 
To characterize the serum PK of ponsegromab following a single SC administered dose in healthy adult Chinese participants.	Primary: 
Ponsegromab serum PK parameters (unbound and total), as data permit: AUC_{inf}, AUC_{last}, C_{max}, T_{max}, and $t_{1/2}$.
Secondary: 
To evaluate the safety and tolerability of ponsegromab following a single SC administered dose in healthy adult Chinese participants.	Secondary: 
Adverse events (AE), clinical safety laboratory tests, vital signs (blood pressure, pulse rate), physical examinations, and 12-lead ECGs for approximately 18 weeks post single dose.

Figure 1 consists of a 2x4 grid of bar charts. The top row is labeled 'Objectives' and the bottom row is labeled 'Endpoints'. The columns are labeled with four categories: 'A', 'B', 'C', and 'D'. Each category has two bars: a black bar for 'CCI' and a white bar for 'CCI+'. The 'CCI+' bars are generally taller than the 'CCI' bars, indicating higher values. The bars are grouped by category, with 'A' on the far left and 'D' on the far right of each row.

2.3. Study Design

This is an open-label, single dose study to characterize the PK, CCI safety, and tolerability of ponegromab following 100 mg or 400 mg single SC dose in healthy adult Chinese participants.

The study will enroll 2 cohorts of approximately 18 healthy adult Chinese participants (N=9 for each cohort).

Participants who meet eligibility criteria at baseline will receive a single SC dose of ponsegrromab at 100 mg (Cohort 1) or 400 mg (Cohort 2) on Day 1. Participants in the 100 mg cohort will be dosed firstly, and will be kept under safety monitoring for 8 days at the clinical research unit (CRU). Progression to 400 mg will occur only if 100 mg is well tolerated after reviewing the safety data up to 8 days post-dose as judged by the investigator. Sentinel dosing may be implemented in the 400 mg cohort as judged by the investigator: eg, 2 participants may be dosed prior to the remaining participants in Cohort 2. If the dose level is determined to have an acceptable safety and tolerability profile up to 8 days post-dose, as judged by the investigator for the first 2 sentinel participants, the remaining 7 participants in that cohort will be dosed. The total duration of each participation in this study is approximately 22 weeks, including a screening period of up to 4 weeks to confirm eligibility and a follow-up period of approximately 18 weeks after the single SC dose.

3. ENDPOINTS AND BASELINE VARIABLES: DEFINITIONS AND CONVENTIONS

As listed in [Section 2.2](#) the primary and the other endpoints are related to ponsegromab serum PK and are described herein.

Samples for the PK analysis of ponsegrumab will be taken according to the schedule of activities (SoA) given in the protocol.

PFIZER CONFIDENTIAL

Ponsegromab serum PK parameters (unbound and total) will be derived (if data permit) from the concentration-time profiles using standard non-compartmental methods as detailed in Table 2. Actual PK sampling times will be used in the derivation of ponsegromab serum PK parameters (unbound and total). In the case that actual PK sampling times are not available, nominal PK sampling times will be used.

Table 2. Ponsegromab Serum PK Parameters (unbound and total)

Parameter	Definition	Method of Determination
C_{\max}	Maximum serum concentration	Observed directly from data
CC1		
T_{\max}	Time for C_{\max}	Observed directly from data as time of first occurrence
$t_{1/2}^a$	Terminal half-life	$\log_e(2)/k_{el}$, where k_{el} is the terminal phase rate constant calculated by a linear regression of the log-linear concentration-time curve
AUC_{last}	Area under the serum concentration-time profile from time zero to the time of the last quantifiable concentration (C_{last})	Linear/Log trapezoidal method
CC1		
AUC_{inf}^a	Area under the serum concentration-time profile from time zero extrapolated to infinite time	$AUC_{\text{last}} + (C_{\text{last}}/k_{el})$, where C_{last} is the predicted serum concentration at the last quantifiable time point estimated from the log-linear regression analysis
CC1		

a. As data permit.

3.1. Primary Endpoint(s)

The primary endpoints are below ponsegromab serum PK parameters (unbound and total):

- AUC_{inf} , AUC_{last} , C_{\max} , T_{\max} , and $t_{1/2}$.

3.2. Secondary Endpoint(s)

The secondary endpoints include safety endpoints, which are described in [Section 3.5](#).

CC1

[REDACTED]

[REDACTED]

[REDACTED]

[REDACTED]

[REDACTED]

[figure not shown]
[REDACTED]

CCI

10.1007/s00332-010-9000-2

100% of the time, the *labeled* and *unlabeled* data are drawn from the same underlying distribution.

■ XXXXXXXXXX

1 

■ XXXXXXXXXX

3.4. Baseline Variables

There are no baseline variables to be used as covariates or stratification factors in this study.

Baseline values are those collected on Day 1 prior to dosing, or the last pre-dose measurement collected on Day -1.

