| Safety laboratory tests h   | X                 | X |                                    |       | X     | X     | X     |        | X             | X         | X         | X         | X         |           | X X        |
| CCI   |                   |   |                                    |       |       |       |       |        |               |           |           |           |           |           |            |
|  |                   |   |                                    |       |       |       |       |        |               |           |           |           |           |           |            |
| Blood Sample (s): serum ponsegromab (PK)   |                   |   | X i                     | X     | X     | X     | X     | X      | X             | X         | X         | X         | X         | X         | X X        |
| Urine drug test  | X                 | X |                                    |       |       |       |       |        |               |           |           |           |           |           |            |
| COVID-19 test(s) j  | X                 |   |                                    |       |       |       |       |        |               |           |           |           |           |           |            |

- Participants will admit to CRU at least 12 hours prior to dosing. Admission procedures to be conducted once, unless deemed necessary by investigator or sponsor.
- FU to approximately 18 weeks postdose planned; FU visits may be adjusted at investigator/sponsor discretion, including to monitor open AE, or based on emerging data (see [Section 4.4](#)).
- Medication history will be updated at each visit.
- Full PE at Screening or admission; at all other timepoints, limited PE performed for findings during previous exam or new/open AEs, at investigator discretion. PE may be conducted at final FU visit, at investigator discretion. Body weight to be measured at all indicated timepoints.
- Injection site assessment at predose (-30 min to 0 h), and 1 h (±10 min), 6 h (±0.5 h), 12 h (±1 h) and 24 h (±2 h) postdose. Additional assessments at investigator discretion and/or until any symptoms resolve. Additional requirements see [Section 8.2.2](#).
- Baseline ECGs should be triplicate collections at 60 min (±5 min) predose, 30 min (±5 min) predose, and 15 min (±5 min) predose (nine measurements in total). Additional requirements on ECGs see [Section 8.2.4](#).

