### 2.1. Study Rationale

This study is the first clinical study with ponsegromab in the Chinese population. The purpose of this study is to evaluate the PK, PD, safety, and tolerability of ponsegromab following 100 mg and 400 mg single subcutaneous dose in healthy adult Chinese participants. Ponsegromab exhibits target mediated disposition, in addition to non-specific catabolism, which is considered to be less susceptible to ethnic factors. Results from this study will be used to preliminarily support the ethnic sensitivity assessment between Chinese and Westerners, to inform clinical development of ponsegromab in China, to facilitate China's participation in global pivotal studies, and to support China registration of ponsegromab.

[figure not shown]

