#### 4.2. Scientific Rationale for Study Design

This study is the first clinical study with ponsegromab in the Chinese population. The study is designed as open-label, with PK in healthy adult Chinese participants as the primary objective. The safety and tolerability **CCI**

██████████ will be investigated as secondary **CCI**

The intended route of administration of ponsegromab to patients is SC; the same route will be tested in this study.

[figure not shown]
As is typical for early development studies, and to allow better comparisons in PK, PD, safety, and tolerability of ponsegromab between Chinese and non-Chinese, the population envisioned for this China Phase 1 study will be similar to that in studies C3651001 and C3651002, ie, healthy male and female participants. Female participants will be confirmed to be categorized as women of non-childbearing potential as, at the present time, embryo-fetal developmental toxicology studies with ponsegromab have not been conducted. In male participants, appropriate measures to minimize potential transfer of ponsegromab via semen to partners are expected to be followed (see [Appendix 4](#)).

Risks to study participants will be minimized by dose administration in an inpatient setting, with careful assessment and on-going review of safety data. After single-dose SC administration, there will be a follow-up period of approximately 18 weeks. This duration has been chosen based on the PK half-life of ponsegromab observed in the completed clinical trials **CCI** ██████████ Clinical safety laboratory tests (see [Section 8.2.5](#)), thorough assessments of vital signs, ECGs, physical examinations, and AE monitoring will provide essential data to evaluate the safety and tolerability of ponsegromab.

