**CCI**  
██████████

populations including global Phase 1 study (C3651001), Japan Phase 1 study (C3651002), and the current China Phase 1 study (C3651012) are all designed as single dose. Serial PK samples will be collected following single dosing to generate PK parameters which allows comparison among different ethnic populations.

[figure not shown]
CCI

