#### **4.3. Justification for Dose**

[figure not shown]
Participants enrolled will receive a single 100 mg or 400 mg SC dose of ponsegromab on

CCI

Specifically, the 400 mg is expected to cover the potential highest clinical dose in subsequent

CCI

direct comparison of ponsegromab exposure cross three different populations (Chinese, Westerners, and Japanese).

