### **6.5. Dose Modification**

By design, this study only includes administration of single, SC dose of ponsegromab at 2 fixed dosage levels (100 mg and 400 mg). As such, dose modifications will not be made during the study.

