5.2. General Methods

All data will be descriptively summarized.

Binary and categorical variables will be presented using summary statistics: number of observations and percentages.

Continuous variables will be presented using summary statistics: number of observations, arithmetic mean, standard deviation (SD), coefficient of variation (cv%), median, minimum, maximum, geometric mean and geometric cv%.

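### Does the intended ethnic PK comparison require the SAP to adjust for body weight and print confidence intervals?

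*SAP*

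**What the plan says.** The stated primary objective (Protocol Section 3, SAP Section 2.2) is to characterize serum PK after one SC dose in healthy Chinese adults. There is no hypothesis, and Protocol Section 9.5 says the sample size has no statistical decision rule behind it.

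The protocol also names a later use. Section 2.1: "Results from this study will be used to preliminarily support the ethnic sensitivity assessment between Chinese and Westerners". The text after Section 4.2 adds: "Serial PK samples will be collected following single dosing to generate PK parameters which allows comparison among different ethnic populations". Section 4.3, partly redacted, speaks of a "direct comparison of ponsegromab exposure cross three different populations". On comparability, Section 4.2 says "the population envisioned for this China Phase 1 study will be similar to that in studies C3651001 and C3651002", meaning healthy men and women; weight is not mentioned.

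Dosing is flat at 100 mg or 400 mg (Protocol Section 6.5). Eligibility is weight above 50 kg with BMI 17.5 to 30.5 kg/m² (Section 5.1). The schedule footnote reads "Body weight to be measured at all indicated timepoints", which covers screening, admission and the outpatient visits.

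SAP Section 3.4: "There are no baseline variables to be used as covariates or stratification factors in this study". SAP Section 5.2: "All data will be descriptively summarized", with N, mean, SD, cv%, median, range, geometric mean and geometric cv% for continuous variables. SAP Table 3 shows the same statistics for Cmax and AUCinf, a shorter set for Tmax and t½, and no confidence interval. Individual parameter values are listed (SAP Section 6.1), and baseline characteristics are summarized (SAP Section 6.5.1). Several PK parameter rows and analysis paragraphs are redacted.

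**The concern.** With a flat dose, lighter people tend to reach higher exposure. If Chinese participants are lighter on average than those in the Western study, raw geometric means placed side by side would mix a weight difference with any ethnic one. Weight is measured before dosing, yet no visible PK analysis uses it.

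With about 8 evaluable per cohort, a point estimate shown without an interval also invites over-reading. At stake would be the use of the results for China development and registration: a modest difference could be read as ethnic sensitivity, or a real one dismissed.

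**Working it through.** **1. The plan's own figure.** Protocol Section 9.5 gives 9 enrolled and 8 evaluable per cohort. 2 × 9 = 18 and 2 × 8 = 16, an implied non-evaluable share of 1 − 16/18 = 11.1%. The figures agree with each other. No CV, margin or target precision is given, so no precision claim exists to reproduce.

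**2. Can a reader recover the interval?** On the log scale σ = √ln(1 + CV²), and the 90% limits for a geometric mean are the estimate times exp(± t(0.95, n−1) × σ/√n). The inputs are N and geometric cv%, both reported. The CV is not in the documents, so 20% to 50% is assumed. With n = 8, t(0.95, 7) = 1.895. At CV 30%, σ = √ln(1.09) = 0.294, the half-width is 1.895 × 0.294/√8 = 0.197, and the factors are 0.82 and 1.22.

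**3. Ratio to a comparator study.** The factors are exp(± t(0.95, 14) × σ × √(1/8 + 1/8)), assuming a comparator group of 8 with the same CV; t(0.95, 14) = 1.761.

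| Assumed CV | Geometric mean, n = 8 | Ratio, 8 vs 8 |
|---|---|---|
| 20% | 0.876–1.142 | 0.840–1.191 |
| 30% | 0.821–1.217 | 0.772–1.295 |
| 40% | 0.773–1.294 | 0.712–1.404 |
| 50% | 0.729–1.372 | 0.660–1.516 |

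The first interval column follows from the planned tables. The second needs the comparator's data, which this SAP does not handle.

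**4. Size of a weight effect.** Suppose exposure varies as weight to the power −e. The ratio from weight alone is then (comparator weight / Chinese weight)^e. Neither weights nor e are in the documents. Assuming 65 vs 80 kg:

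- e = 0.5: (80/65)^0.5 = 1.109
- e = 0.75: (80/65)^0.75 = 1.169
- e = 1: 80/65 = 1.231

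Assuming 70 vs 80 kg, e from 0.5 to 1 gives 1.069 to 1.143.

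**5. Would weight normalization repair it?** Multiplying each exposure by weight/70 sets e to 1 and multiplies the cross-study ratio by 65/80:

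- true e = 0.5: 1.109 × 65/80 = 0.90
- true e = 0.75: 1.169 × 65/80 = 0.95
- true e = 1: 1.231 × 65/80 = 1.00

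The bias is removed only at e = 1; otherwise it changes sign. Even then, the comparator studies must be normalized in the same way, which a SAP for this study cannot arrange.

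**6. Where confounding could arise.** Inclusion criterion 2 makes every participant Chinese, so ethnicity is constant. No covariate used within this study can separate weight from ethnicity. That is possible only in an analysis holding both populations.

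**The case for a change.** An interval is a descriptive statement and needs no hypothesis. With no statistical basis for the sample size, it is the natural way to show what 8 per cohort can support. Under the assumptions above, a plausible weight effect (7% to 23%) is of the same order as the sampling uncertainty. SAP Section 5.3.2 lets a summary appear with as few as 3 values; at CV 30% the 90% factors are then 0.61 to 1.64, and AUCinf and t½ are available only where the data allow. Modeling is mentioned in Protocol Section 9.4 and SAP Section 7.1, but no visible text says how weight will enter it or which document governs the comparison. The additions would cost a few table rows and one figure.

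Much of this stands. The visible SAP prints no interval, does not name weight in its baseline summary, and points to no cross-study plan. Printed 90% intervals, baseline weight by cohort, and a plot of log exposure against weight with no fixed exponent would help the reader.

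The step from there to a defect does not stand. SAP Section 3.4 prohibits nothing: with no model in the visible plan there is nothing for a covariate to enter, and a pooled analysis elsewhere remains free to use weight. The interval is left out but not concealed, since its ingredients and the individual values are reported. Protocol Section 2.1 calls the ethnic support preliminary. Absence of weight-related content also cannot be asserted for the redacted rows; Protocol Table 1 does show a dose-normalized Cmax, so normalized parameters are not foreign to this plan, though that does not show weight normalization is among them.

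**Conclusion.** No change to the plan is called for. Followed as written, it gives sound descriptive PK for its stated objective. Weight becomes an issue only in the later comparison with studies C3651001 and C3651002, where an analyst holding all the data can adjust for it using weights already collected here.

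The intervals for Cmax and AUCinf follow from statistics already planned: factors of 0.88–1.14 at CV 20% to 0.73–1.37 at CV 50%, with n = 8. The potential weight effect, 7% to 23%, rests on assumed mean weights (65 or 70 vs 80 kg) and an assumed exponent of 0.5 to 1; the documents support none of these values. Proportional normalization would leave a spurious ratio of 0.90 to 0.95 in the 65 vs 80 kg case if the true exponent is 0.5 to 0.75, so its gain is doubtful. The additions are a reporting preference and would alter no planned estimate.
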